1.0 BACKGROUND AND HYPOTHESES

There are an estimated 1.2 million people who inject drugs (PWID) in the US.^{29,30} Injection drug use dramatically increases risk for blood borne infectious diseases, endocarditis, soft tissue infections, drug overdose, psychiatric disorders, and mortality.³¹⁻³⁸ Despite this, there are few interventions to prevent drug injection initiation, and we are not aware of any that have been proven to be efficacious in a rigorous, large randomized controlled trial (RCT).³⁹⁻⁴³

To address this critical public health need, we propose to conduct a large-scale RCT of "Change the Cycle" (CTC)^{.7,44} an hour long, single-session, one-on-one intervention that aims to reduce injection initiation by encouraging active PWID to not promote drug injection, model injection behavior, describe how to inject, or assist in injection initiations of non-injectors. This approach is informed by social learning theory, which postulates that people learn behaviors through interaction, observation, behavioral experimentation, and reinforcement.^{1,2} These constructs are all highly relevant to the prevention of injection initiation; existing research convincingly demonstrates that *interactions* with active PWID who describe injection, observations of injection drug use, and *reinforcing* conversations that promote the advantages of drug injection (e.g., the better "high" to be gained from injecting) contribute to injection initiation.⁴⁵⁻⁵⁶ Further, retrospective accounts of injection by an active PWID.^{48,57} Therefore, intervening on active PWID to reduce describing how to inject to non-injectors (*interaction*), injecting in front of non-injectors (observation), speaking positively about injection drug use (*reinforcement*), and assisting in first injection (*experimentation*) could be a promising approach for reducing uptake of injection drug use.

CTC uses the Information-Motivation-Behavioral skills (IMB) model^{3,4} to achieve changes among active PWID through seven short modules. Information and motivational domains are addressed in guided conversations about (1) their own first injection episode and consequences, (2) past experiences initiating injection-naive people and consequences, (3) health, legal, and social risks related to injection drugs, (4) health, legal, social risks of initiating people, and (5) identifying their own behaviors that might promote injection among others. The behavioral skills domain is addressed through a (6) skill-building discussion and rehearsal of responses to possible initiation scenarios, and (7) safer injection education. CTC pilot study results found significant reductions in injection initiation episodes; however, the study did not have a control group.⁷ Our specific aims are:

Aim 1: To test the efficacy of CTC on reducing the number of non-injectors initiated into injection (counts) by PWID. *Hypothesis 1*: PWID who receive CTC will report initiating fewer non-injectors into drug injection at 6 and 12 months as compared with PWID in the equal attention control condition.

Aim 2: To test the efficacy of CTC on reducing the number of times PWID are asked to initiate (counts) someone into injection. Hypothesis 2: PWID who receive CTC will report having been asked fewer times to initiate someone into drug injection at 6 and 12 months as compared with PWID in the equal attention control condition.

Aim 3: To test whether injection initiation social learning risks (injecting in front of, describing injection to, and speaking positively about injection to non-injectors) act as mediational mechanisms for the efficacy of the CTC intervention on initiation and request-to-initiate outcomes. Hypothesis 3: Social learning variables will significantly mediate the association between the CTC intervention and episodes of initiating and being requested to initiate someone into drug injection at 6 and 12 months.

Following completion of 12-month follow-up interviews, we will collect elucidation interviews with up to 100 PWID for purposes of providing preliminary data on key issues related to 1) Hepatitis A and C risk, needs, and services collected through a quantitative survey, and 2) experiences with drug effects and withdrawal and symptoms management in a qualitative audio-recorded interview.

The elucidation interview topics were selected to investigate key issues related to health promotion among PWID. A brief justification for each topic is provided below. 1) HCV/HAV module: A recent outbreak of HAV in Los Angeles highlighted the inadequacy of both sanitation services (toilets and showers) for homeless populations in Los Angeles and HAV vaccination interventions

(http://publichealth.lacounty.gov/eprp/Health%20Alerts/DPH%20HAN%20Hep%20A%20Outbreak%20091917. pdf). Items related to the HAV will include access to toilets and showers, HAV vaccination, and preferences for sanitation services for homeless PWID. New direct-acting HCV treatments are now available, but inducing and completing treatment for PWID has proven to be difficult. Items on knowledge, attitudes, beliefs, and preferences for HCV treatment will be asked of participants. 2) Drug effects and withdrawal module: Anaylses of our prior study data (2011-13) indicated that polyroute (injection and non-injection -71%) and polysubstance (use of two or more illicit substance – 70%) use was common in our sample, yet little is known about reasons for specific drug use combination and/or sequences. To begin to understand these common phenomena, we will ask open-ended items on common drug use combinations and sequences and elicit reasons for using substances in these combinations or sequences. Lastly, preliminary data from the baseline interviews indicate that withdrawal symptoms in the last 6 months were reported by 85% of eligible heroin users and 54% of methamphetamine users. Management of withdrawal symptoms by PWID has not been extensively studied and may related to polyroute and polysubstance use behaviors. We will ask open-ended (i.e., qualitative) questions about how PWID handle withdrawal symptoms when they occur. Study resuls will contribute to efforts to address HAV and HCV infections and to inform substance use treatment approaches. Participants will be offered the opportunity to complete the Hepatitis survey and the qualitative interview separately. We have developed separate consent forms for each. Participants will be selected by convenience and data collect for the separate modules will not be linked together or linked to the parent study. Participants will be given \$10 to complete each module.

2.0 OBJECTIVES AND PURPOSE

To achieve these aims, people who inject drugs (PWID) who report having initiated someone or having injection initiation social learning risks in the past 6 months (N=1,076) will be randomly assigned to receive CTC or an equal attention control condition in Los Angeles (LA) and San Francisco (SF), CA. Injection initiation

and injection initiation social learning variables will be collected at baseline, 6 months, and 12 months. CTC is brief, easy to implement, and novel in its focus on active PWID as a conduit for preventing injection initiation. If proven efficacious, CTC will be a much-needed, practical approach to preventing drug injection initiation.³⁹⁻⁴³

The main outcomes by Aim are as follows: 1) Counts of non-injectors initiated into drug injection at 6 and 12 months; 2) Counts of request to initiate a non-injector into drug injection at 6 and 12 months; and 3) Counts of noninjectors initiated into drug injection and request to initiate non-injectors at 6 and 12 months. The study will be implemented in 2 phases. Phase 1 involves adaptation and training of intervention personnel and Phase 2 involves implementing the full study.

Elucidation goals are to better understand issues related to 1) HAV/HCV effects and 2) drug effects and withdrawal and symptoms management PWID.

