Aim 1: To test the efficacy of CTC on reducing the number of non-injectors initiated into injection (counts) by PWID. Hypothesis 1(H1): PWID who receive CTC will report initiating fewer non-injectors into drug injection at 6 and 12 months as compared with PWID in the equal attention control condition. To test H1, we will conduct structural equation modeling (SEM) using Mplus (release 7.11).99 Our primary outcome analysis is based on an outcome that is distributed as counts of the number of episodes initiating someone into drug injection. This is a standard Poisson count variable with a potential inflation of the number of zeros as there will likely be many who do not initiate others (e.g., zero-inflation). This Poisson count outcome can essentially be thought of as consisting of two separate, yet interrelated, processes-one in which the participant engaged in the behavior of initiating someone else at all (i.e., binary yes/no) and another in which we assess the number of times the participant initiated someone (ranging from 1 to j, where j=the number of episodes initiating someone. In SEM literature, this is referred to as a two-part process for zero inflated Poisson, as SEM models these two processes separately as unique latent processes.¹⁰⁰ As this outcome is collected as part of an intervention with a baseline (T0) and two follow-ups (T1, T2), the model is parameterized to accommodate three time points, following Olsen and Schafer (2001).¹⁰⁰ Note that with three time points, the implied model is mis-identified given the number of measured variables in the variance-covariance from the observed data in an SEM measurement model with an intercept (i) and slope (s) for 3 observations.¹⁰¹⁻¹⁰³ However, joint modeling the ZIP as a two-part process redresses the identification problem, and results in 6 measured variables, one for the process in which the participant actually initiated another person (0 for no, 1 for yes) and another for the

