change/reduction in the number of initiations over the 3 observation times (1 to i). The first part of the analysis will involve characterization of the measurement model for the change over time from T0 to T1 and from T1 to T2. As shown in Figure 3, the model will include a treatment covariate representing the effect of the CTC intervention on changes over time for the binary (sU) and count (sZ) latent variables, and it may contain other covariates identified as having been distributed differentially by condition at baseline or associated with loss to follow-up. Note that if there are no differences at baseline in preliminary bivariate analyses, there is no need to include a treatment effect on the intercept for the SEM because with no differences at baseline, the intercept test for difference is likely to be non-significant so there is no value in risking the extra degrees of freedom. Through model constraints, we will also examine specific differences between conditions within time points (e.g., T1 or T2) and between time points (e.g., change over time from T0 to

Figure 3. Two-Part Zero-Inflated Poisson SEM

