T1). There will be little need for additional covariates to control for potential inflation of the correlations due to recruitment sites, as the targeted sampling will ensure full coverage across the locations where PWID congregate in LA and SF. We will, however, explore differences between the two sites, and may introduce a control variable to account for large-scale environmental differences between the two sites. To avoid any analytic decisions being driven by a desire for a certain result, the statistician and data analysis team will be blinded as to whether 0 or 1 denotes the treatment or control condition until the analyses are completed. There is also potential for contamination, which we will assess by asking the respondents in the control condition their level of exposure to intervention components, as described in Section 3.5.17.3. We will follow procedures outlined by Keogh-Brown et al. (2007) using complier average causal models (CACE),¹⁰⁴ in which the bias associated with contamination is significantly reduced by averaging the estimated causal effect over classes of participants that differ in the level of exposure to contamination. Each person in the control group will be assigned to a class, depending on their level of exposure and type of exposure, using latent classification techniques utilized by [name] in previous publications.¹⁰⁵ Lastly, we will compare differences in examining the rate of change versus the standardized difference at each follow-up point (e.g., compare counts of injection initiation at 6m and 12m) and test for differences by condition. The latent change model has more power than the raw difference approach, and we will present differences in our published work if the outcome is sensitive to model estimation.

Aim 2: To test the efficacy of CTC on reducing the number of times PWID are asked to initiate (counts) someone into injection. H2: PWID who receive CTC will report having been asked fewer times to initiate someone into drug injection at 6 and 12 months as compared with PWID in the equal attention control condition. This model will be estimated in the same manner as the model for the outcome of the actual number of reported counts, save that this one will estimated using the self-reported counts by the respondent regarding being asked to initiate another person.

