Aim 3: To test whether injection initiation social learning risks (injecting in front of, describing injection to, and speaking positively about injection to non-injectors) act as mediational mechanisms for the efficacy of the CTC intervention on initiation and request-to-initiate outcomes. H3: Social learning variables will significantly mediate the association between the CTC intervention and episodes of initiating and being requested to initiate someone into drug injection at 6 and 12 months. The outcome variable will remain counts of the number of episodes initiating someone into drug injection (Aim 1) and the counts of request to initiate another person (Aim 2). The mediational models will be specified following the work of Baron and Kenny and newer generalizations.¹⁰⁶⁻¹⁰⁸ With only three time points, we can examine the effect of baseline randomization to treatment status on 12-month counts of injection initiation as the outcome and 6-month injection-risk behavior variables as the mediators. The lagged approach can be used as static measures at 6 months and 12 months, or changes in injection initiation social learning risks and IMB skills constructs that precede changes in the number of counts of initiation as outcome. This latter approach is strong in that the change in a variable, created by difference scores, is isolated so that it precedes the subsequent outcome.

There are also techniques for estimating mediational models with only 2 time-points;¹⁰⁹ consequently, we will examine mediation from randomization to 6-month follow-up with the mediator and outcome measured concurrently. We can estimate separate mediational models for each injection initiation social learning risk and IMB skills construct, or enter the mediation mechanisms together into a single model, while examining overfit due to multiple mediational paths.¹¹⁰ Omnibus measures of model fit (chi-square, root mean square error of approximation, Tucker Lewis Index [TLI]), and specific path coefficients will be used to assess the treatment effect and test for the mediational pathways. The null hypothesis will be rejected if the p value for the variable that denotes treatment condition is below 0.05. Proposed Co-I [name] has extensive experience with these techniques as part of longitudinal community-based interventions.^{105,111,112}

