13.2. Sample size/ power analyses

Power calculations were estimated using Mplus by creating a Monte Carlo Simulation by generating a synthetic data set based on the expected parameter values, such as slopes, standard errors, and correlations among measured variables, for the anticipated treatment effect.^{113,114} Power was estimated assuming an intracluster correlation of 0.5, which is similar to our previous NIDA-funded studies.^{105,112,115} Statistical tests were two-sided, allowing detection of effects in either direction, and an alpha of .05 and power at 80%, corresponding to moderate effect sizes. Because the outcome is a count (i.e., Poisson), standard errors were estimated as non-normal via a sandwich estimator in Mplus.¹¹⁶ Co-Is [name] and [name] found that the number of participants who initiated people into injection was halved at follow-up.⁷ Preliminary data from MPIs [name] and [name]'s study in LA and SF indicated that 809 active PWID were found to have initiated 431 people in the past year. Using the same proportion, we expect that 573 people would be initiated by our proposed sample size of 1,076 participants at baseline (286 in each arm). If the number of people initiated by intervention group participants is halved, as suggested by [name] and [name]'s pilot data, that would represent a reduction of 143 people not being initiated into injection.

We also calculated the effect under different assumptions of attrition, subgroups (e.g., 25% Latino), sex, and age. For brevity, we illustrate power for primary outcome and most conservative—changes in the number of injection initiation events. We also account for 25% attrition—our worst-case scenario. To test the three hypotheses given our alpha and power specifications, we would need a baseline recruitment of 1,076 (n=538 per condition). We will recruit 1,076 participants to achieve the final sample of approximately 800 at the 12-month data point. The sample power for Cohen's effect sizes for small (2 percentage point difference), medium (5% difference) and large (10%–15% difference) effect sizes are plotted in **Figure 4**, revealing that after

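### H1 and H2 are both main outcomes at 6 and 12 months, tested at an unadjusted 0.05, with no deciding visit, testing order or either/both rule

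*Combined protocol and SAP*

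**What the plan says.** - **Outcomes.** Section 2.0 opens its list of main outcomes with "Counts of non-injectors initiated into drug injection at 6 and 12 months; 2) Counts of request to initiate a non-injector into drug injection", the latter also at 6 and 12 months. Requests to initiate (H2) therefore have the same main-outcome status there as initiations (H1), at the same two visits.
- **Hypotheses.** Section 13.1 words H1 as "PWID who receive CTC will report initiating fewer non-injectors into drug injection at 6 and 12 months". H2 has the same form for requests, and its model is to be estimated in the same way. Section 1.0 presents both aims as tests of efficacy.
- **Primary label.** The Aim 1 text in 13.1 and the power text in 13.2 call the initiation outcome primary. No testing rule is attached to that label.
- **Contrasts.** The main model puts the treatment effect on two slopes, one for the binary part and one for the count part. In addition, "we will also examine specific differences between conditions within time points (e.g., T1 or T2) and between time points". A final step is to "compare counts of injection initiation at 6m and 12m" as raw differences and test them by condition.
- **Threshold.** The only rejection rule is in the Aim 3 text: "The null hypothesis will be rejected if the p value for the variable that denotes treatment condition is below 0.05". Section 13.2 specifies two-sided tests at alpha .05 and says "To test the three hypotheses given our alpha and power specifications, we would need a baseline recruitment of 1,076".
- **Time point of the power.** Section 13.2 also says "We will recruit 1,076 participants to achieve the final sample of approximately 800 at the 12-month data point", and its stated powers refer to those 800 participants at 12 months.

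**The concern.** The plan offers at least four between-arm comparisons that could each be read as showing that CTC works: two outcomes at two visits. It does not say which one decides. If a significant result at either visit, on either outcome, supports a claim, the stated alpha of .05 is not what the trial delivers. If both visits must be significant, alpha is protected, but the chance of success is lower than the power at a single visit.

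This matters in practice because the intervention is a single one-hour session whose effect could fade. A result significant at 6 months but not at 12, or the reverse, is quite possible. It would count as success under one reading and failure under the other, and the reading would be settled after the data were seen. The problem is separate from the choice between the binary and count slopes and from the mediation tests. It would remain with one treatment coefficient per outcome and visit.

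**Working it through.** **Inputs from the documents**
- Two main outcomes at two visits, so 4 contrasts (2.0, 13.1).
- Two-sided alpha 0.05, no adjustment (13.1, 13.2).
- Stated power with 800 participants at 12 months: 0.82 small, 0.88 moderate, 0.99 large effect (13.2). Target power 80%.
- 25% attrition, 1,076 recruited (13.2).

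**Input not in the documents.** The correlation between the test statistics, across visits and across outcomes, is not given. It is assumed, and varied from 0 to 0.9. The intracluster correlation of 0.5 in 13.2 is a different quantity and does not support any value here.

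**The plan's own figures.** The sample size reproduces: 800 / (1 − 0.25) = 1,067, and 1,076 × 0.75 = 807, or about 800. The plan states no familywise error rate. Its powers cannot be rebuilt because no control rate is given.

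**Step 1: either visit counts, H1 alone (2 tests).** P(at least one |Z| > 1.96) under no effect:
- independent: 1 − 0.95² = 0.0975
- bivariate normal: 0.095 at correlation 0.3, 0.091 at 0.5, 0.083 at 0.7
- in CTC's favour only, at 0.5: 0.045, against 0.025 for one test

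**Step 2: either visit, H1 or H2 (4 tests).** P(at least one |Z| > 1.96) under no effect:
- independent: 1 − 0.95⁴ = 0.185
- multivariate normal simulation, 2 million draws:

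| Common correlation | Either direction | In CTC's favour |
|---|---|---|
| 0 (exact) | 0.185 | 0.096 |
| 0.3 | 0.174 | 0.087 |
| 0.5 | 0.156 | 0.078 |
| 0.7 | 0.130 | 0.065 |
| 0.9 | 0.094 | 0.047 |

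With 0.5 between visits, 0.5 between outcomes and their product for the cross terms, the values are 0.161 and 0.081.

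**Step 3: both visits required, H1.** Each hypothesis keeps its error at or below 0.05. For power, take a stated power as the power at each visit (an assumption). The noncentrality is 1.960 + z(power).
- 0.82 per visit: 1.960 + 0.915 = 2.875. P(both significant) = 0.71 at correlation 0.5 (0.70 at 0.3, 0.74 at 0.7). P(exactly one) = 2 × (0.82 − 0.715) = 0.21 (0.25 to 0.16).
- 0.88 per visit: 1.960 + 1.175 = 3.135. P(both significant) = 0.80 at correlation 0.5 (0.79 at 0.3, 0.82 at 0.7). P(exactly one) = 2 × (0.88 − 0.802) = 0.16.

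**The case against.** Five points deserve weight.

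1. **H1 is labelled primary**, in 13.1 and again in 13.2, and each outcome belongs to its own aim. A reader might infer that H1 and H2 are wholly on a par; the documents do not support that. On the strict view only the H1 figure of about 0.09 applies. This stands as far as it goes. But the label brings no order or alpha rule, section 2.0 still calls requests a main outcome, and the two-visit question remains for H1 by itself.
2. **The main model is a growth model**, with treatment acting on change over all three time points. The visit contrasts come afterwards, and 13.1 regards the latent-change approach as the more powerful. True, but the hypotheses are worded by visit, and nothing makes the visit contrasts descriptive.
3. **A reader might infer that the chance of a false claim that CTC works is 0.16 instead of 0.05.** That is not supported. The tests are two-sided, so 0.16 includes false findings of harm. The matching pair for a claim in CTC's favour is about 0.08 against 0.025. The value also needs an assumed correlation near 0.5 and the either-visit reading, which the text permits but does not state.
4. **A reader might infer that requiring both visits necessarily breaks the 80% power target.** It does so with 0.82 per visit. It does not with 0.88, the stated power for the moderate effect to which 13.2 ties its 80%.
5. **Safeguards exist.** The analysis team is blinded to arm coding until analyses are complete, and differences are to be published if the result is sensitive to model estimation. These reduce the risk of deliberate selection. They neither control alpha nor say which visit decides.

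**Conclusion.** The point holds in this form: two main outcomes and two visits, an unadjusted two-sided 0.05, conflicting main and primary labels, and no deciding visit, order or either/both rule.

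If either visit counts, the any-direction error is about 0.09 for H1 alone (0.083 to 0.095 for correlations 0.7 to 0.3). For H1 and H2 together it is about 0.16 at correlation 0.5, within 0.09 to 0.185 over the whole range tried. In CTC's favour the figures at correlation 0.5 are about 0.045 and 0.08 against 0.025, so roughly two and three times nominal.

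If both visits are required there is no inflation within a hypothesis, and H1 power is about 0.71 or 0.80 according to which stated power is used.

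All these sizes rest on assumed correlations and approximately normal test statistics. The power figures also treat the stated powers as per-visit powers. The absence of a decision rule depends on none of these assumptions.

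**What to change.** In 13.1:
1. Name one deciding contrast for H1 from the planned longitudinal model: the CTC versus control difference in initiation counts at 12 months, tested at two-sided 0.05. This is the time point to which the power in 13.2 refers.
2. Test the same 12-month contrast for H2 at two-sided 0.05 only if step 1 is significant.
3. Report the 6-month, between-time-point and raw-difference contrasts with 95% confidence intervals, labelled descriptive.
4. Make the main and primary labels agree across 1.0, 2.0, 13.1 and 13.2.

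The fixed sequence holds the H1/H2 family at 0.05 without splitting alpha.

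**Cost.** Wording only, with no extra participants or data. H2 becomes confirmatory only after H1 succeeds, and an effect seen only at 6 months is no longer a confirmatory claim.

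**Alternative.** A contrast combining the 6- and 12-month reports is possible, but it is more than a wording change. It departs from the planned growth-model contrast and needs a rule for a missing report under the expected 25% attrition. It also needs a rule for recall windows that overlap or leave gaps, since section 3.12 lets interviews take place up to one month late.
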